9.2. Subject Screening

Subjects may be recruited through the investigator's practice and referring physicians.

Potential subjects may be identified through chart reviews or as new or existing patients attend clinic visits as appropriate. If subjects are recruited from outside the investigator's practice, sites are to ensure that appropriate release for access to the subject's records (paper and/or electronic) is obtained. Any subject recruitment materials disseminated to subjects (advertisements, handouts, posters, social media) must be approved by the IRB/EC prior to use.

All subjects must be consented in accordance with the protocol prior to any study-specific procedures. Recruited subjects will be screened by the Principal Investigator or authorized site personnel by reviewing the study's inclusion and exclusion criteria.

A screening log should be completed by the site to maintain a cumulative log of all screened subjects with reason for screening failure.

The Investigator will maintain a listing of all subjects enrolled in the study.

9.4. Subject Consent

The informed consent process will be performed in accordance with the ethical principles that have their origin in the Declaration of Helsinki, 21CFR§50 Protection of Human Subjects (US only), SOR/98-282 (Canada only) and in accordance with local regulatory requirements. No vulnerable patients will be allowed to be consented to participate in the study. Data will be collected and treated in accordance with applicable Data Privacy Legislation. With regard to the EU this includes Directive 95/46/EC and subsequent legislation.

Prior to entering the study, the Principal Investigator or qualified designee will explain to each subject the purpose and nature of the study, procedures, expected study duration, available alternative therapies, and the benefits and risks involved with study participation and the potential treatment. The person obtaining consent will avoid any coercion or undue improper influence on, or inducement of, the subject to participate and the ICF will not waive, or appear to waive, any legal rights. Subjects will be given a copy of the IRB/EC approved ICF and will have ample time to review the document and to ask questions and will be informed of their right to withdraw from the study at any time without prejudice; ICFs will be provided in a language understandable to the subject. After this explanation and before any study-specific procedures have been performed, the subject will voluntarily sign and personally date the

Medtronic Confidential

ICF. Prior to participation in the study, the subject will receive a copy of the signed and dated written informed consent and any other written information provided to the subject.

The Principal Investigator or qualified (delegated) designee will document the informed consent process, including the date of consent and name of the person conducting the consent process in the subject's medical record. A copy of the signed ICF will also be placed in the subject's medical record. Throughout study participation, any significant new information will be provided to the subject as outlined in the informed consent form. As appropriate, the ICF may be revised based on new information that becomes available.

9.5. Randomization and Treatment Assignment

Once the subject meets all eligibility criteria for the study, and has a successful therapy evaluation, site personnel may proceed with the neurostimulator device implant and randomization procedures. If a subject does not meet all eligibility criteria, subjects should be exited and not proceed to the neurostimulator device implant and randomization procedures.

At the time of the device implant, site personnel will obtain randomization for one of the following therapy amplitudes: sensory threshold, 50% of sensory threshold or 80% of sensory threshold. Randomization will be assigned in a 1:1:1 ratio, and stratified by site. Site personnel will obtain the subject's randomization sequence on the Randomization eCRF which will be generated from the database.

The investigator and research staff at the study site will be instructed to keep the subject blinded to their randomization; however, subjects may or may not feel stimulation. The outcome measures in this study are based on the subject's own assessment. Therefore, keeping the subject blinded to their randomization reduces bias in the outcome measurement reporting. [REDACTED]

During the study, subjects will be encouraged to remain in the randomized treatment arm; however, a subject may request to be re-programmed with a different amplitude setting. If this occurs, a protocol deviation will be required and subjects should continue in the study and complete the remaining follow-up visits.

[REDACTED]

[REDACTED]

9.7. Assessment of Efficacy

Subject assessments will be performed by appropriately trained, qualified and delegated site personnel according to the usual practices of the site.

Urinary Voiding Diary

Symptoms related to OAB will be evaluated using paper voiding diaries. Subjects will be trained to complete the urinary voiding diaries for 3-days as part of the baseline and therapy evaluation procedures. The voiding diaries will be completed at baseline, therapy evaluation and prior to the 6 and 12-week follow-up visits. Every effort should be made to remind subjects of the importance of real-time diary completion.

Voiding diary data will be used to verify study inclusion criteria for UUI episodes at baseline. Diaries will also be used for comparison of efficacy from 12-week follow-up visit to baseline for the primary study endpoint of UUI [REDACTED]

Assessments for Quality of Life Measures

Subjects will complete the study questionnaires confidentially on paper forms without site personnel consultation and these data will be entered to OC/RDC by site personnel. Questionnaires should be completed prior to the follow-up visit when data is collected. Site personnel are encouraged to review forms for completeness.

ICIQ-OABqol Questionnaire

The ICIQ-OABqol is a robust, patient-completed questionnaire for evaluating quality of life (QoL) in patients with overactive bladder, for use in research and clinical practice.⁹ The questionnaire used in the current study includes 26 questions which are 4-week recall for symptom assessment.

[REDACTED]

[REDACTED]

[REDACTED]

9.8. Assessment of Safety

9.8.1 Reportable Adverse Events and Device Deficiencies

All reportable adverse events and device deficiencies will be collected throughout the study once the informed consent form is signed.

9.9. Recording Data

This study will be conducted using a remote data capture system. The Oracle Clinical Remote Data Capture (RDC) system which allows the study centers to enter study data into the sponsor's database over a secure internet connection, will be used to capture study required Case Report Form (CRF) information. Data reported on voiding diaries and subject questionnaires will be entered to the database by site personnel. Subjects will complete the study questionnaires confidentially on paper forms without site personnel consultation and these data will be entered to OC/RDC by site personnel. Electronic CRFs (eCRFs) will be provided by the sponsor; required data will be taken from source documents and directly entered into the study database via the CRFs by the site personnel, in accordance with applicable regulations.

Device interrogation (programming) data may be transmitted using either NPU or by manual data entry on a programming CRF.

Subject voiding diaries and questionnaires are to be completed only by the subject. Representatives from the research site may not make entries to the diaries or questionnaires except for administrative clarification on source documentation.

The Principal Investigator, Sub-Investigator, or an individual delegated by the Principal Investigator on the Delegation of Authority and Signature Form, are responsible for documenting and entering data for the study on the eCRFs. The Principal Investigator or Sub-Investigator is required to approve all data on CRFs via electronic signature.

9.10. Deviation Handling

Protocol deviations are digressions from the written protocol defined as an event where the clinical investigator or site personnel did not conduct protocol-required procedures according to the study protocol. Protocol deviations are to be preapproved by Medtronic study personnel and the IRB/EC (as required) unless the deviation is necessary to protect the health, safety, or welfare of a subject in an emergency situation. The investigator or delegated site personnel should contact the designated Medtronic study personnel to discuss the impact of the potential deviation; prior approval of deviations should be documented. Prior approval is generally not required if the deviation is due to an emergency circumstance or an unforeseen circumstance that is beyond the investigator's control; however, these deviations should be reported to Medtronic and the IRB/EC (as required) after site personnel become

aware of the deviation. Site personnel should work with subjects to ensure subject follow-up visits are scheduled within the visit window; however, any visits completed outside of the visit window will require a protocol deviation to be reported. All protocol deviations must be reported on the Protocol Deviation eCRF after the site's awareness of the deviation.

The sponsor may choose to terminate the study at a site for failure to follow the written protocol and investigator agreement. If this occurs, the Investigator, IRB/EC and governing regulatory authority (if applicable) will be notified in writing of the reasons for the termination.

9.11. Subject Withdrawal or Discontinuation

Subjects are free to voluntarily withdraw from the study at any time and for any reason. All implanted subjects will be followed until the 12-week follow-up visit, unless withdrawn from the study. Withdrawn or exited subjects will be followed under normal medical practice.

Examples of reasons for study discontinuation include, but are not limited to, those listed below:

- If the subject does not meet eligibility criteria of at least 3 UUI episodes demonstrated on a 3-day baseline urinary voiding diary
- Subject death
- Subject lost to follow-up
- Subject voluntarily withdraws from the study
- Subject becomes pregnant
- Investigator terminates the subject's participation in the study due to lack of compliance, violation of/change in eligibility criteria
- Any clinical laboratory abnormality, current illness, or other medical condition or situation occurs such that continued study participation would not be in the best interest of the subject.
- Subject is not a candidate for InterStim Therapy
- Normal study completion

Prior to deeming a subject lost to follow-up, telephone calls must be documented in the subject's medical record. If a minimum of three attempts to contact the subject have failed (e.g. phone and mailed letter), and no response is received, the site should exit the subject and complete the Study Exit eCRF.

When a subject is withdrawn from the study, the Study Exit eCRF is to be completed and should include detailed notes as to why the subject was withdrawn from the study (e.g., discomfort, lack of efficacy, diary too burdensome). Withdrawn subjects will not be replaced.

Once a subject completes participation in the study, follow-up will continue in accordance with the site's standard of care. No study specific medical care will be provided for a subject after discontinuation from the study, unless outlined in the Clinical Trial Agreement and Informed Consent Form.

10. Risks and Benefits

10.1. Potential Risks

The risks outlined below are the same risks found in commercial InterStim II System use; however, based on the amplitude settings, subjects may experience less than desired improvements in OAB symptoms. No additional study specific risks are present.

10.1.1. Risks Outlined in the Instructions for Use (IFU)

Refer to the appropriate Instructions for Use (IFU) for the InterStim System components for updated list on contraindications, precautions, warnings, adverse events, directions for use and other product specific details.

In addition to the risks normally associated with surgery, implantation, or use of a neurostimulation system includes, but is not limited to, the following risks. Certain adverse events may necessitate surgical intervention.

- Adverse change in voiding function (bowel and/or bladder)
- Allergic or immune system response to the implanted materials that could result in device rejections
- Change in sensation of stimulation which has been described as uncomfortable (jolting or shocking) by some patients
- Infection
- New pain
- Pain at neurostimulator and or lead site
- Seroma, hemorrhage, hematoma
- Suspected lead or neurostimulator migration or erosion
- Suspected nerve injury
- Suspected technical device problem
- Transient electric shock

The safety of SNM has not been established for pregnant women, for an unborn fetus, or during childbirth. This precaution is provided in the InterStim Therapy commercial labeling and should be adopted in this study; thus, no one who is pregnant or planning to become pregnant will be enrolled.

If a subject learns or suspects that she is pregnant, the investigator will instruct her to turn her neurostimulator OFF and to visit the study site as soon as possible; however, this will not be considered a reportable AE.

10.2. Potential Benefits

Subjects may not receive any direct medical benefit from participation in this study but subjects will receive additional medical oversight of treatment. Participation in this study may not provide greater benefit than if the subject was receiving InterStim Therapy outside of the study, as required study programming is within approved programming specifications. Information from this study might help researchers further understand InterStim Therapy related to uncomfortable stimulation. The benefit to subjects participating in this study, and to future patients, resides in the knowledge gained from this study.

10.3. Risk-Benefit Rationale

Participation in this study will not expose the subject to greater risks than if he/she were receiving InterStim Therapy outside of the study. There might be other discomforts and risks related to InterStim Therapy and/or this study that are not foreseen at this time. In addition, based on the amplitude settings, subjects may experience less than desired improvements in OAB symptoms.

The risks associated with InterStim II System are minimized in this study by selecting only qualified Investigators experienced in InterStim Therapy, selecting an appropriate patient population via inclusion/exclusion screening, and monitoring subject progress and events reported for this study. The review and minimization of the potential risks to the patient and the potential benefits to the patient support the conduct of this study.

11. Adverse Events and Device Deficiencies

11.1. Definitions/Classifications

Any adverse event meeting the definition of: serious, device related, therapy related and/or procedure related as well as all device deficiencies will be considered reportable for this study. The term “investigational device” is part of ISO14155 definitions. The term “investigational device” refers to any device used in the study including market released devices. Adverse events and device deficiencies are defined as follows:

- **Device Related:** An adverse event that results from the presence or performance (intended or otherwise) of the InterStim II System
- **Procedure Related:** An adverse event that occurs due to any procedure related to the implantation or surgical modification of the InterStim II System. The procedure is defined as the lead placement or implant procedure.
- **Therapy Related:** An adverse event related to therapy delivery by device e.g. device stimulation issue (normally therapy-related events resolve when the device is turned off or reprogrammed).

Table 11-1: Adverse Event & Device Deficiency Definitions

Term	General
Adverse Event (AE) (ISO 14155:2011 3.2)	Any untoward medical occurrence, unintended disease or injury, or untoward clinical signs (including abnormal laboratory findings) in subjects, users or other persons, whether or not related to the investigational medical device. NOTE 1 This definition includes events related to the investigational medical device or the comparator. NOTE 2 This definition includes events related to the procedures involved. NOTE 3 For users or other persons, this definition is restricted to events related to investigational medical devices.
Adverse Device Effect (ADE)* (ISO 14155:2011 3.1)	Adverse event related to the use of an investigational medical device. NOTE 1 This definition includes adverse events resulting from insufficient or inadequate instructions for use, deployment, implantation, installation, or operation, or any malfunction of the investigational medical device. NOTE 2 This definition includes any event resulting from use error or from intentional misuse of the investigational medical device.
Device Deficiency (DD)* (ISO 14155:2011 3.15) (ISO 14155:2011 3.27)	Inadequacy of a medical device with respect to its identity, quality, durability, reliability, safety or performance. NOTE 1 Device deficiencies include malfunctions, use errors, and inadequate labeling. 
 ▪ Malfunction: Failure of an investigational medical device to perform in accordance with its intended purpose when used in accordance with the instructions for use or CIP

(ISO 14155:2011 3.43)
	
 ▪ Use Error: Act or omission of an act that results in a different medical device response than intended by the manufacturer or expected by the user 
NOTE 2 Use error includes slips, lapses, mistakes.
 
NOTE 3 An unexpected physiological response of the subject does not in itself constitute a use error.

SERIOUSNESS
	

Serious Adverse Event (SAE)* (ISO 14155:2011 3.37)
	
Adverse event that
 
 a) led to a death, b) led to a serious deterioration in the health of the subject, that either resulted in: 
 1. a life-threatening illness or injury, or 2. a permanent impairment of a body structure or a body function, or 3. in-patient or prolonged hospitalization, or 4. medical or surgical intervention to prevent life-threatening illness or injury or permanent impairment to a body structure or a body function. c) led to foetal distress, foetal death or a congenital abnormality or birth defect. 
NOTE Planned hospitalization for pre-existing condition, or a procedure required by the CIP, without serious deterioration in health, is not considered a serious adverse event.

Serious Adverse Device Effect (SADE)* (ISO 14155:2011 3.36)
	
Adverse device effect that resulted in any of the consequences characteristic of a serious adverse event

Unexpected Serious Adverse Device Effect (USADE)*
	
Serious adverse device effect which by its nature, incidence, severity or outcome has not been identified in the current version of the risk analysis report

(ISO 14155:2011 3.42)	NOTE Anticipated serious adverse device effect (ASADE) is an effect by which its nature, incidence, severity or outcome has been identified in the risk analysis report.
RELATEDNESS	
Relationship of Adverse Events	
The relationship of the adverse event to the study treatment (device, therapy, procedure) will be described using the following terms:
 
 • Not related • Unlikely • Possible • Probable • Causal relationship

*Reportable event categories that will be collected during this study

11.2. Report of Adverse Events

Any adverse event meeting the definition of serious, device-related, procedure-related and/or therapy-related as well as all device deficiencies as defined above will be considered reportable for this study.

The following are not adverse events:

- Transient effects that occur during the implant procedure or programming and resolve without reprogramming.
- Any normal expected postoperative complaints or symptoms unless the event involves a clinically significant change in severity or duration of symptoms or requires clinical intervention that is different from ordinary postoperative care. Expected postoperative outcomes include headache, incisional pain, nausea, vomiting, low grade fever, oozing at dressing, dizziness, irritability, sleepiness, nervousness, insomnia, constipation, urinary retention, confusion and similar events.
- Worsening of OAB symptoms will be collected as part of the efficacy measures and are not considered a reportable adverse event.

For reporting of all serious adverse events and/or serious adverse device effects, the following emergency Sponsor contact may be used:

Phone: 1[contact]

Email: [contact]

Address: [name]

All reportable adverse events will be classified using the following responsibility matrix:

Table 11-2 Event Classification Responsibilities

What is Classified	Who Classifies	Classification Parameters
Relatedness	Investigator	Procedure related Device related Therapy related
USADE potential	Medtronic	USADE
Seriousness	Investigator	SAE/SADE
Diagnosis	Investigator	Based on presenting signs and symptoms and other supporting data
	Medtronic	MedDRA term assigned based on the data provided by investigator

All reportable adverse events must be recorded in the subject's medical record and on an Adverse Event and/or Device Deficiency eCRF and promptly reported to Medtronic based on Table 11-2. IRB/EC reporting must be completed in accordance with the policies of the governing IRB/EC. Governing regulatory authority reporting should be completed in accordance with applicable local regulations.

Reports of adverse events and device deficiencies will include the following information, at a minimum:

- Date of event
- Diagnosis or description of the event
- Assessment of the seriousness and relationship to the product(s) under study
- Treatment
- Outcome and date of resolution

It is the responsibility of the Investigator to identify the occurrence of reportable adverse events and device deficiencies and to ensure the required information is accurately documented on the eCRF.

The clinical course of each adverse event must be followed until resolution or subject discontinuation from the study, whichever comes first. "Ongoing" adverse events and device deficiencies must be assessed at each protocol required visit, and new or updated information must be documented on the Adverse Event and/or Device Deficiency eCRF and promptly reported to Medtronic and if applicable to the IRB/EC. Commercial medical device reporting processes will be followed for complaint handling.

If necessary, the Investigator may report to the sponsor initially by telephone or email and follow-up with completed eCRFs and, if possible, copies of source documentation regarding the event (e.g., physician/nurse notes or summaries).

Medtronic study personnel will promptly review all reported adverse events and device deficiencies and

Medtronic Confidential

if necessary request clarification and/or additional information from the Investigator. If Medtronic disagrees with the Investigator's assessment of the adverse event relationship to device, therapy and/or procedure, Medtronic study personnel will document the disagreement and report or ensure reporting of both opinions to IRB/EC as necessary. All reported adverse events and device deficiencies will be reviewed by a Medtronic Medical Advisor to ensure consistent reporting

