The therapy evaluation period should be conducted in accordance with the InterStim II System Labeling. The therapy evaluation period must not exceed either 14 days if using InterStim tined lead or 7 days if using the temporary Test Stimulation Lead as defined by current labeling, or a new approved duration in an updated commercially available labeling in the respective country. A 3-day voiding diary will be completed towards the end of the therapy evaluation period. A minimum of a 50% improvement in UUI or UF voiding symptoms, or return to normal voiding of < 8 voids per day for UF subjects, is required in order to qualify for a neurostimulator implant in the study. Settings used during therapy evaluation will be documented during this visit. Any [REDACTED] reportable adverse events/device deficiencies will be documented and reported.

Tined Lead (if applicable) / Neurostimulator Device Implant (randomization procedures)

Once the subject qualifies for the neurostimulator device implant, site personnel may proceed with the neurostimulator device implant and randomization procedures. If a subject does not qualify for the neurostimulator device implant, they will be exited from the study.

For subjects who qualify for device implant following a successful basic evaluation, the InterStim tined lead should be placed in accordance with the InterStim Therapy Model 3889 Lead Implant Manual.

[REDACTED]

At the time of the neurostimulator device implant, site personnel will obtain a randomization assignment to randomize each subject to one of the following therapy amplitudes: sensory threshold, 50% of sensory threshold or 80% of sensory threshold. Subjects are blinded to their randomization. All measures should be taken to ensure that the subject does not become unblinded to their randomization throughout the study.

Subjects will be implanted with the Neurostimulator in accordance with the InterStim Therapy InterStim II Model 3058 Neurostimulator Implant Manual.

After the device implant is complete, it is required that subjects be programmed to 14 hertz (Hz), 210 μ s pulse width (pw) and continuous stimulation for the duration of the study. During programming, the subject's sensory threshold amplitude will be determined by following this protocol: start at 0.05 volts (V) and increase voltage using fine resolution in 0.05 V increments until the subject reports sensation.

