The subject is exited from the study after the 12-week follow-up visit is complete. Programming parameters after the subject has completed the study are at the Investigator's discretion.

Unscheduled Visit

If an unscheduled visit is needed for any device-related reason, the subject's sensory threshold amplitude will be confirmed by following this protocol: start at 0.05 V and increase voltage in 0.05V increments until the subject reports sensation. Prior to the completion of the study, the amplitude at each electrode configuration that elicits a sensory response must be determined in [REDACTED] seated [REDACTED] [REDACTED] positions. To determine sensory threshold, each electrode (0,1,2,3) will be programmed as the cathode (negative) in a bipolar configuration in a systematic fashion.

Following determination of sensory threshold amplitude, amplitude will be programmed based on the assigned randomization using the sensory threshold in a seated position. Subjects will be allowed to adjust amplitude +/- 0.05 V during the trial. As part of the programming, impedance checks should be completed. Upon completion of programming, data will be collected via a programming printout or NPU.

All efforts should be made to maintain subject in the randomized arm. If the subject must be changed from their randomized arm, subjects should be encouraged to complete a 3-day voiding diary prior to the unscheduled visit.

[figure not shown]
In addition to programming activities, any [REDACTED] reportable adverse events and device deficiencies will be collected.

Surgical Revision

If a surgical revision is required after the full system implant, the subject will be exited from the study.

Figure 9-1: Study Visits illustrates required study visits for basic and advanced evaluations:

Figure 9-1: Study Visits

InterStim Amplitude Clinical Investigation Plan

MDT17030

Version 2.0

Page 29 of 61

Table 9-1: Study Procedures

	Enrollment / Baseline	Tined Lead or Test Stimulation Lead Implant	Therapy Evaluation	Tined Lead (if applicable)/ Neurostimulator Device Implant	1-Week Follow-Up Visit (+/- 3 days)	6-Week Follow-Up Visit (+/- 7 days)	12-Week Follow-Up Visit (+/- 7 days)	Unscheduled Visit
Informed Consent	X*							
Randomization Procedures				X***				
Relevant Medical History	X							
ICIQ-OABqol Questionnaire	X						X	
Pregnancy Assessment	X							
[REDACTED]		[REDACTED]		[REDACTED]				
Assessment of Sensory Threshold		X		X	X	X	X	X
PGI-I Questionnaire						X	X	

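### Adverse event follow-up may stop at study exit and surgical revision forces exit, so the resolution of the event and any complication of the revision need not be recorded

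*Protocol*

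**What the plan says.** Protocol Section 11.2 gives the rule for ending follow-up: "The clinical course of each adverse event must be followed until resolution or subject discontinuation from the study, whichever comes first". Section 9.1 (Surgical Revision), repeated in the synopsis, gives the exit rule: "If a surgical revision is required after the full system implant, the subject will be exited from the study". Section 9.11 leaves exited subjects to routine care, and the readable text has no safety contact after exit.

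Other parts of the protocol expect more. Section 10.1.1 acknowledges that "Certain adverse events may necessitate surgical intervention". Section 11.1 defines a procedure-related event, which is reportable, as "An adverse event that occurs due to any procedure related to the implantation or surgical modification of the InterStim II System". The minimum content of an event report in Section 11.2 includes the outcome and resolution date, and Section 14.2 also lists the resolution date.

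A second exit occurs before randomization. Section 9.1 states: "If a subject does not qualify for the neurostimulator device implant, they will be exited from the study". These subjects already have a test or tined lead in place.

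On the analysis side, SAP Sections 7.9.3.1 and 7.10 report number of events, number of subjects and percent of subjects. For events after neurostimulator implant, SAP Section 7.10.7.3 takes the randomized subject set as the denominator for the by-group summary.

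**The concern.** Each rule is ordinary alone, but in combination the occurrence that ends follow-up can be the consequence of the event being followed. A subject whose device or procedure event requires revision is exited because of it. From then on the study has no stated duty to record how the event ended, what happened at the revision, or whether the revision caused a further event.

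Safety is a listed additional measure, summarized by amplitude group. The subjects affected are those with the device events that most need a complete record, and the arms are small enough for one missing subject to show in the tables. The planned narratives of serious adverse device effects (SAP Section 7.10.5) could also lack an ending.

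**Working it through.** **1. The rules applied to one case.** This is a hypothetical randomized subject with a device-related event in week 4 that requires revision.

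| What happens | Recorded by the study? | Basis |
|---|---|---|
| Onset, diagnosis, seriousness, relatedness, treatment | Yes | Protocol 9.8.1 and 11.2: onset is before exit |
| Resolution in week 6 | Not required | 11.2: follow-up may stop at discontinuation; 9.1: exit for revision |
| Complication of the revision in week 7 | No stated collection | 11.1 classes it as procedure-related, but the subject has left |
| Place in the post-implant denominator | Kept | SAP 7.10.7.3 |

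**2. Direction of the effect.** Reported incidence is subjects with an event divided by subjects randomized. Exit can remove later events from the numerator and never adds any, and the denominator is fixed. The readable text has no exposure adjustment. Incidence is therefore either unchanged or too low, compared with collection to week 12.

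**3. Which figures move.** The event that triggers the revision is already counted, so if it is related, the percent of subjects with any related event does not change. The number of events can change. So can the percent within a category, because SAP Section 7.10.2 tabulates device-, therapy- and procedure-related events separately and by MedDRA term. In the case above, the subject is counted as device-related and may be missed as procedure-related.

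**4. The plan's own numbers** (Protocol 13.1.1, SAP 6: 42 completers, 14 per arm, 10% attrition, 80% evaluation success).
- Per arm: 14 / (1 − 0.10) = 15.6, rounded up to 16; 16 × 3 = 48. This reproduces the stated figure of about 48. Working from the total gives 42 / 0.90 = 46.7, or 47, which is consistent.
- Enrolled: 48 / 0.80 = 60, as stated.

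**5. How many subjects could be affected.**
- One subject in an arm of 16: 1 / 16 = 6.25 percentage points.
- Exits after implant for any cause: 48 × 0.10 = 4.8, about 5; or 48 − 42 = 6 if exactly 42 complete. If the attrition allowance holds, revision exits are some unknown part of these 5 to 6 across three arms.
- Exits before implant: 60 − 48 = 12. This is an upper bound on non-qualifiers with a lead placed, because Protocol Section 6 says the 60 also allows for screen failures.

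The documents give no rate of surgical revision, so the number of truncated records cannot be calculated.

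**The case against.** The case for leaving the plan alone has real content.

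- **Most of the information is collected.** Reportable events are captured from consent, ongoing events are reassessed at each required visit, the sponsor may ask for more information, and the Study Exit eCRF needs detailed notes. This stands, and it limits the loss to the course, outcome and new events after exit.
- **The tables do not report outcomes.** The visible SAP counts events and subjects, and the triggering event is already in the count. This also stands. What remains is under-counting of new related events after exit, and event reports without the outcome the protocol asks for.
- **Exit timing is not stated.** Nothing says the subject leaves before the operation. If the exit form is completed afterwards, the revision itself may be captured. But the protocol does not require that, and later complications would still fall outside.
- **An open event can be reported as ongoing.** That softens the conflict with the required resolution date but leaves the outcome unknown.
- **There are other routes.** Commercial complaint handling runs in parallel, and Table 14-1 requires European investigators to report new information on a serious event already reported. Neither is said to apply after exit in a way that updates the study database.
- **Context.** This is an on-label feasibility study with descriptive safety summaries. That argues for a light remedy.

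Several SAP safety sections are redacted (7.10.1, 7.10.4, 7.10.6, 7.10.7.1 and 7.10.7.2) and cannot be judged. They belong to the analysis plan; the collection rule is in Protocol Section 11.2.

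**Conclusion.** The point holds for surgical revision. The rule on ending follow-up and the rule on exit allow a revision-triggering event to close its own study record, which does not fit the plan's definition of procedure-related events or its minimum report content. Any effect on post-implant incidence is downward. Its size is unknown: one subject is 6.25 percentage points in an arm of 16, and revision exits cannot exceed the 5 to 6 post-implant exits if the 10% attrition allowance is right. The conclusion assumes that exit ends study data collection, which is the natural reading of Sections 9.11 and 11.2, and that no redacted text says otherwise.

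A reader might infer more in four ways that the documents do not support.

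- *That outcomes of important device events are never collected.* Everything with onset before exit is collected, including any outcome reached by then.
- *That failing the therapy evaluation is also a safety-triggered exit.* It is an efficacy rule: "A minimum of a 50% improvement in UUI or UF voiding symptoms", or a return to normal voiding for urgency-frequency subjects. The readable text does not say when a tined lead is removed relative to exit, so this group raises only a record-keeping question.
- *That non-qualifiers dilute the safety rates.* They are not in the randomized set, and no readable passage makes the test subject set a safety denominator.
- *That pregnancy is a parallel gap.* It is not a device event and is only an example of a reason for discontinuation. The statement "however, this will not be considered a reportable AE" concerns the pregnancy itself, not a foetal outcome that meets the serious event definition. Following pregnancies could also run months past a participation of about 16 weeks.

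**What to change.** Reconcile Protocol Section 11.2 with Section 9.1 (Surgical Revision) and the matching synopsis text, Section 11.1 and Section 14.2, by separating exit from efficacy and randomized-amplitude assessment from the end of safety data collection. State that:

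1. Subjects exited for surgical revision stay in collection of reportable adverse events and device deficiencies to their planned 12-week date.
2. Any serious or device-, procedure- or therapy-related event open at exit is recorded to resolution or to a stated cut-off date.
3. For non-qualifiers who had a lead placed, lead removal and any open related event are recorded before the Study Exit eCRF is closed.

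This is a data-collection rule and leaves clinical management as the protocol states it. The cost is protocol wording and a few extra telephone or chart contacts: on the plan's figures, at most 5 to 6 subjects after implant, plus a closing record for up to 12 non-qualifiers. The 12-week date lies within planned participation, so only events still open at exit could extend collection, and the cut-off limits that.
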